## **8.2 Baseline**

Baseline data will only be collected after the subject has agreed to participate and signed an informed consent form. Baseline data collected will include: hospital transfer, age, sex, vital signs (height, weight, blood pressure, respirations, etc), pertinent medical history, pre-treatment NIHSS, pre-stroke Modified Rankin Score, neuroimaging results, and thrombolytic therapy.

## **8.3 Mechanical Thrombectomy Procedure**

To be eligible to participate, the procedure had to begin within 8 hours of stroke onset with planned first line therapy of the use of the Q Aspiration Catheter alone.

Digital subtraction angiography should have been undertaken to verify vessel occlusion using diagnostic angiography and contrast agent. Repeat diagnostic angiography should have been done on the treated region to assess recanalization grade per mTICI criteria after Q Catheter use and at the end of the procedure.

The Q Aspiration Catheter must be used per the Instructions for Use to be eligible for participation. Per the IFU, the Q Aspiration Catheter may be used with three aspiration attempts.

Procedural data collection will include:

- General procedural data (anesthesia use, procedure start time, revascularization time and end time, thrombolytic therapy administered, ancillary device use)
- Target vessel location
- Pre-and post-procedure target vessel flow information
- Q Aspiration Catheter use during the procedure
- Rescue device use, if applicable
- Treatment outcome
- Embolization to a new territory
- Procedure and device-related adverse events or any device related problems
- De-identified procedural angiogram should be collected for the Core Lab (only after subject consent) (see Section 11.7)

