## **6 STUDY POPULATION**

### **6.1 Study Population**

The observational study population is patients diagnosed with large vessel occlusion acute ischemic stroke within 8 hours of stroke onset treated with mechanical aspiration thrombectomy with the Q Aspiration Catheter as first line therapy. The Q Aspiration Catheter must be used according to the IFU to be included in the study. All study candidates (or legal representative) must be able to provide written informed consent and agree to be followed at 3 months post-procedure.

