### **6.3 Inclusion Criteria**

Subjects who meet the following criteria may be included in the study:

1. Age 18 to 85 years;
2. Diagnosis of acute ischemic stroke with mechanical thrombectomy procedure < 8 hours from onset of symptoms or last known well;
3. Large Vessel Occlusion on CT scan or MRI in the Anterior Cerebral Vasculature up to A1, M1, M2, or Posterior Cerebral Vasculature;
4. ASPECTS 6 – 10 or volume of diffusion restriction < 50 mL;
5. Use of the Q Aspiration Catheter as the first line treatment according to the IFU;
6. Signed informed consent by patient or legally authorized representative.

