# **8 STUDY PROCEDURES**

## **8.1 Screening and Enrollment**

All patients diagnosed with acute ischemic stroke who undergo mechanical thrombectomy with the Q Aspiration Catheter as first line therapy, without regard to gender, are eligible for screening to participate in the clinical study. Patients will be screened based on the study inclusion and exclusion criteria after the procedure.

A screening log should be kept of all subjects in whom the Q Aspiration Catheter was used to prevent bias in subject selection. Death may be added to the screening log as reason for screen failure, if applicable.

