## **10.2 Statistical Methods**

This study is a single arm, registry study with endpoints compared to well defined and published outcomes. This study is designed for observational data to be collected and reported. There will be no formal statistical hypothesis testing conducted, and therefore sample size is not based on power calculations.

Data analysis will comprise of descriptive statistics (means, standard deviations, rates, correlations, etc.) on the variables detailed in the study endpoints and other data collected.

The analyzed population will consist of all subjects who signed an informed consent form.

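### Entry rests on planned first-line Q alone in one sentence of 8.3 but on actual use elsewhere, so a Q that never reaches the clot can be missing from both the study and the screening log

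*Combined protocol and SAP*

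**What the plan says.** All references are to the combined protocol and SAP.

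- **8.3, opening sentence.** For eligibility, "the procedure had to begin within 8 hours of stroke onset with planned first line therapy of the use of the Q Aspiration Catheter alone". This is a rule about intent and exclusivity.
- **8.3, later sentence.** "The Q Aspiration Catheter must be used per the Instructions for Use to be eligible for participation". This is a rule about actual use.
- **6.3 criterion 5, and the same line in the synopsis.** "Use of the Q Aspiration Catheter as the first line treatment according to the IFU". Actual use, without *planned* or *alone*.
- **6.1.** Patients "treated with mechanical aspiration thrombectomy with the Q Aspiration Catheter as first line therapy". Actual treatment, again without either word. Section 8.1 also speaks of patients who undergo thrombectomy with the Q first line.
- **8.1, timing and log.** "Patients will be screened based on the study inclusion and exclusion criteria after the procedure", and "A screening log should be kept of all subjects in whom the Q Aspiration Catheter was used".
- **10.2.** "The analyzed population will consist of all subjects who signed an informed consent form". No hypothesis test is planned, and results are to be compared with published outcomes.
- **4.3 and 13.2.** The secondary performance endpoint is mTICI 2b-3 after the Q alone in 4.3. Its definition in 13.2 leaves out *alone*.
- **13.3.** Another device counts as rescue only after the study device has failed to recanalize.

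No section says whether *use* means opened, introduced, positioned at the clot, or aspirated through.

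**The concern.** Reaching the clot is part of what the device has to do; section 3.1 presents access to more distal clot as a potential advantage. A patient in whom the Q is introduced as planned, cannot be advanced to the occlusion, and is then treated with another device meets the intent rule in 8.3. The same patient was arguably not treated by aspiration with the Q (6.1), and a site may judge that there was no first-line use (6.3).

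That judgement is made after the procedure, when the angiographic result is known. If the answer is no, the patient is not enrolled and need not appear on the screening log, because the log depends on the same undefined word. The analysis set in 10.2 takes in whoever consented and cannot restore the case. The Q-alone rate would then be conditional on successful access, and a comparison with published rates would rest on a denominator that is not known.

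**Working it through.** The plan gives no rate, access-failure count or power calculation to reproduce. The check is a comparison of the texts, followed by denominator arithmetic on assumed counts.

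**Step 1. Three cases under three readings.**

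Case A: Q alone planned, Q introduced, clot not reached, no aspiration. Case B: first pass planned as Q plus another device. Case C: Q alone planned, but the first pass becomes combined.

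| Reading | A | B | C |
|---|---|---|---|
| 6.3 criterion 5 only | out if *use* means treatment or aspiration; in if introduction counts | can be in | in |
| 6.3 together with all of 8.3 | same as above | out | in |
| Intent sentence of 8.3 only | in | out | in |

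The status of A depends on which sentence is applied and on what *use* means. B is settled once 8.3 is applied. C passes every reading, and no section says how it is scored for the Q-alone endpoint.

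**Step 2. Q-alone rate.** Let N be planned first-line attempts, x Q-alone successes and k access failures, none of which can be a Q-alone success. The rate is x/N with access failures kept and x/(N − k) with them dropped. The second is larger whenever x and k are above zero.

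Inputs: N = 50, borrowed from the enrolment ceiling in 6.2. The values of x and k are assumptions.

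- x = 27, k = 0: 27/50 = 54.0%
- x = 27, k = 2: 27/48 = 56.3%
- x = 27, k = 5: 27/45 = 60.0%
- x = 27, k = 8: 27/42 = 64.3%

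Over other assumed values:

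| x (x/50) | k = 1 | k = 3 | k = 5 |
|---|---|---|---|
| 30 (60%) | 30/49 = 61.2% | 30/47 = 63.8% | 30/45 = 66.7% |
| 35 (70%) | 35/49 = 71.4% | 35/47 = 74.5% | 35/45 = 77.8% |
| 40 (80%) | 40/49 = 81.6% | 40/47 = 85.1% | 40/45 = 88.9% |

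The upward shift in this grid runs from 1.2 to 8.9 percentage points.

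**Step 3. Final mTICI rate.** This is scored at the end of the procedure, after any rescue. Assume 45/50 = 90.0% and drop 3 access failures.

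- All 3 ended below 2b: 45/47 = 95.7%, higher.
- All 3 were rescued to 2b-3: 42/47 = 89.4%, lower.

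The direction is not fixed.

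**Step 4. Combined first passes.** If m of 50 subjects had a combined first pass scored as a Q result, and their success rate differed by 10 points from the rest, the overall rate moves by m × 10/50 points. For m = 3 that is 0.6 points and for m = 10 it is 2.0 points, in whichever direction the difference lies.

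**The case against.** The strongest reply is that the sections can be read together. The 8.3 sentence is an eligibility condition added to criterion 5, so a planned combined first pass is ineligible under the protocol as a whole, and a site that enrolled one would be deviating. That stands. A reader might infer from 6.3 alone that planned combined passes are admitted, but the documents do not support this. What remains is that the list used at screening does not repeat the condition, and that Case C is not addressed.

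A reader might also infer that every effect favours the device, including on the final revascularization rate. The documents do not support that either. The final rate can move either way (Step 3). Under the 4.3 wording, a combined first pass with no Q-alone reading would not be a success; inflation would need the looser 13.2 wording.

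Further points carry some weight. A Q introduced but not at the clot might be counted as used, and 8.3 itself demands actual use, so the gap lies in the undefined term as much as between sections. The IFU is not in the file and may bear on both matters. Section 8.3 collects device problems and rescue use for enrolled subjects, and 9.3 asks for reports of devices that fail to perform as intended. Those records need not restore an unenrolled patient to the denominator.

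Finally, the study is descriptive and the exact 95% interval at 35/50 is 55.4% to 82.1%, wider than the shifts shown. That limits the practical weight of the point. It does not answer it, because selective entry is a systematic error that the interval does not measure.

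**Conclusion.** The point holds, mainly for one secondary endpoint. The entry rule mixes intent with undefined actual use and is applied after the outcome is known, with a log that depends on the same word. Planned first-line attempts that fail to reach the clot can be left out of both study and log, and no other section brings them back. For a given number of Q-alone successes, the Q-alone rate then rises: 54% to 60% in the main illustration, and by 1.2 to 8.9 points for 1 to 5 dropped cases at assumed rates of 60% to 80%. All these counts and rates are assumptions. The size depends on how often access fails and how sites read *use*, neither of which the documents give. No direction can be claimed for the final mTICI rate or for combined first passes. This is a problem of denominator and endpoint definition, not of sample size. It should be corrected because the remedy is cheap and results are to be set beside published outcomes.

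**What to change.** 1. Put one attempt-based entry rule in the synopsis, 6.1, 6.3 criterion 5, 8.1 and 8.3: a patient is eligible on this criterion when a Q Catheter is introduced into the guide catheter or sheath with the plan to use it alone as first-line therapy.
2. Have the screening log record every such attempt, with a field for whether the clot was reached and the reason for any non-enrolment.
3. Count access failures as Q-alone revascularization not achieved.
4. Repeat *planned* and *alone* in 6.3 criterion 5, so that the exclusion of planned combined first passes already in 8.3 is applied at screening.
5. Restore *alone* in the 13.2 definition of the secondary endpoint, and count a case planned as Q alone that becomes combined on the first pass as Q-alone not achieved.

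The cost is harmonised wording, one extra log field and a slightly less favourable Q-alone rate. These changes concern entry and counting only and alter no patient's treatment.

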### 3.3 Intended Use

The Q Aspiration Catheter is indicated for use in the removal of fresh, soft emboli and thrombi in the peripheral and neurovascular systems. It may also be used as a diagnostic angiographic catheter.

It is intended to be used by physicians skilled in the field(s) Interventional Radiology, Interventional Neuroradiology, Neurosurgery and/or Neurology who are skilled in endovascular interventional procedures for acute ischemic stroke.

The Q Catheter is a family of short, extension catheters that is introduced through an 8F catheter. Aspiration is performed from the short Q and into the 8F catheter. The Q is visible under fluoroscopy and must be hydrated for at least 1 minute in saline prior to use. The Q is typically introduced over a guidewire and is advanced to the desired vessel in the neurovasculature under fluoroscopy. Once in place, tubing attached to a vacuum pump and to the stopcock of an 8F catheter. Thrombus is then aspirated through the Q and into the 8F catheter. At the end of the procedure, all devices are carefully removed and discarded. Device compatibility is in **Table 2** below.

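### Use within the IFU, including its three aspiration attempts, is an entry condition checked after the procedure, so eligibility can depend on how treatment went and the Q-alone success rate may be raised

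*Combined protocol and SAP*

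**What the plan says.** IFU-conforming use is a condition of entry in three places:

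- Section 6.1: "The Q Aspiration Catheter must be used according to the IFU to be included in the study".
- Section 6.3, criterion 5: "Use of the Q Aspiration Catheter as the first line treatment according to the IFU".
- Section 8.3: the catheter "must be used per the Instructions for Use to be eligible for participation".

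The sentence after the last of these names one IFU term: "Per the IFU, the Q Aspiration Catheter may be used with three aspiration attempts". Section 8.1 sets the timing of the check: "Patients will be screened based on the study inclusion and exclusion criteria after the procedure". Earlier in section 8.3, eligibility is instead worded by intention, as a procedure "with planned first line therapy of the use of the Q Aspiration Catheter alone".

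The outcome most affected is the secondary endpoint of mTICI 2b-3 with the Q Catheter alone (sections 4.3 and 13.2). It carries no limit on attempts.

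**The concern.** The number of aspiration attempts is not a baseline feature. It is decided during treatment and is linked to how treatment is going, because the usual reason for a fourth attempt is that three were not enough. If a fourth attempt puts use outside the IFU, and use outside the IFU makes the patient ineligible, then a group made up mainly of poor responders is removed after its result is known.

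The purpose in section 4.1 is to demonstrate safety and performance, section 5.3 says there are no clinical investigation data so far, and section 10.2 sets the endpoints against published outcomes. A Q-alone rate from which some difficult cases had been removed would make that comparison too favourable. The same patients would also be missing from the haemorrhage, embolization, mRS and mortality results.

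**Working it through.** **No plan figure to reproduce.** The sample of up to 50 is expressly not based on power (section 10.2). The documents give no expected Q-alone rate and no share of patients with more than three attempts. Every rate below is an assumption.

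**Step 1: the chain of rules.** IFU use is required for entry (6.1, 6.3, 8.3). The IFU is linked to three attempts (8.3). The check follows the procedure (8.1). Consent also follows the procedure and may be given as late as the 3-month visit (7.2, Table 3), so the attempt count is known before a patient enters. Read as a limit, the rule therefore allows removal on a treatment event.

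**Step 2: effect on success within three attempts.** Let S be the share of all Q-treated patients at mTICI 2b-3 within three attempts, and g the share of the remainder who receive a further attempt and are screened out.

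Observed rate = S / [S + (1 − S)(1 − g)]

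| S | g | Calculation | Observed |
|---|---|---|---|
| 70% | 0% | 0.70 / 1.00 | 70.0% |
| 70% | 10% | 0.70 / 0.97 | 72.2% |
| 70% | 25% | 0.70 / 0.925 | 75.7% |
| 60% | 25% | 0.60 / 0.90 | 66.7% |
| 80% | 25% | 0.80 / 0.95 | 84.2% |

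**Step 3: effect on the endpoint as written.** With no attempt limit in the endpoint, a later Q success counts. If a share h of the screened-out patients succeed later, the true rate is S + (1 − S)gh. With S = 70%, g = 25% and h = 50%, this is 0.70 + 0.30 × 0.25 × 0.50 = 73.75%, against 75.7% observed. The gap is about 2 points, compared with 5.7 when no later attempt succeeds. The true rate is a weighted average of the observed rate (weight 0.925) and h (weight 0.075), so the bias vanishes at h = 75.7% and reverses above that.

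**Step 4: scale at the planned size.** Suppose 35 of 50 enrolled patients succeed (70%, exact 95% interval 55.4% to 82.1%). Putting back k screened-out patients gives (35 + kh) / (50 + k).

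| k | None succeed later (h = 0) | Half succeed later (h = 0.5) |
|---|---|---|
| 2 | 35/52 = 67.3% | 36/52 = 69.2% |
| 5 | 35/55 = 63.6% | 37.5/55 = 68.2% |
| 8 | 35/58 = 60.3% | 39/58 = 67.2% |

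These shifts lie within the sampling interval, but unlike sampling error they would not shrink with more patients.

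**The case against.** A reader might infer that the rule drops failures by construction. The documents do not support that, for four reasons.

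- **Removal is an inference.** The wording is permissive, the IFU is not among the documents, and no section says that a fourth attempt breaches it or makes a patient ineligible. Nor is it said whether the count is per catheter, vessel or patient, and Table 1 lists four catheter sizes. This stands. Even so, the sentence directly follows the eligibility rule, where a limit is its natural reading, and if sites can read it differently it needs clarifying anyway.
- **Most failures may remain.** Rescue therapy is defined in section 13.3 and recorded under section 8.3. A patient who goes to rescue within three attempts is eligible and counts as a Q-alone failure. If nobody exceeds three, the bias is zero.
- **Not everyone removed is a failure.** A patient already at 2b might receive another pass aimed at 2c or 3, and a patient who fails three attempts might succeed later. Both weaken the effect, and Step 2 assumes that all further attempts follow failure.
- **There are partial safeguards.** The screening log should list every Q use, and section 10.2 analyses everyone who signed consent, with no rule for removing someone later found ineligible. Neither restores a patient screened out before consent: section 7.2 bars collecting study data until consent, section 8.3 sends angiograms to the core lab only after it, and no analysis of the log is planned.

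Two further inferences also go too far. The device is "indicated for use in the removal of fresh, soft emboli and thrombi" (section 3.3), but no criterion or procedure excludes patients for clot consistency found during aspiration. And nothing in the documents links repeated passes to extra harm; the supportable statement is only that screened-out patients' safety outcomes go unrecorded.

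Finally, restricting a post-market study to on-label use is a defensible aim. It can be met with a summary of conforming use and does not require exclusion after the event.

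**Conclusion.** The point holds in a limited form. Entry depends on IFU use, the check comes after the procedure, and three attempts is the one IFU term that section 8.3 ties to it. Read as a limit, this can remove patients whose treatment went on because three attempts did not suffice. The likely direction is upward for the Q-alone rate. For the other endpoints the conclusion is only that these patients' results are missing; no direction is claimed.

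The size cannot be derived from the documents. At an assumed 70% success within three attempts, the inflation is 0, 2.2 or 5.7 points when 0%, 10% or 25% of failures receive a further attempt. On the endpoint as written, it falls to about 2 points at 25% persistence if half of the later attempts succeed. It requires that some patients exceed three attempts, that they are screened out for it, and that their late success is below the observed rate. The study is descriptive and the endpoint secondary, so the change is worth making but does not undermine the whole plan.

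**What to change.** 1. Reconcile sections 6.1, 6.3 (criterion 5) and 8.3, so that eligibility rests on planned first-line Q use, as section 8.3 already words it, and on IFU conditions settled before the first aspiration, such as device and guide compatibility.
2. State whether three is a limit under the IFU and how attempts are counted.
3. Record the number of Q attempts on the case report form. Keep patients whose use departed from the IFU during the procedure, and flag them. Section 8.7 should say how such departures are handled, since it currently says only that no deviations will be made.
4. Score the Q-alone endpoint on the angiogram after Q use that section 8.3 already specifies. Scoring on flow after the third attempt is not a safe alternative, because angiography is specified only after Q use and at the end of the procedure.
5. Add a sensitivity analysis that counts patients with more than three attempts as non-successes, and a summary restricted to IFU-conforming use.

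The cost is amendment wording, one case report form item and two extra summaries. Some off-IFU uses will enter the data, and the Q-alone rate may be slightly less favourable. None of this takes a view on how many attempts should be made.

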#### 8.4 Hospitalization

Post procedural data collection will include:

- Neurovascular imaging and NIHSS at day 1 post procedure results (0-36 hour window)
- Serious Adverse Event monitoring including worsening symptoms/new symptoms

Study Investigator should determine if there was an NIHSS increase greater than or equal to 4 points along with neuroimaging (CT or MRI) results showing intracranial hemorrhage, if the subject experiences a symptomatic intracranial hemorrhage.

If available, information on the subject's discharge destination, days in intensive care unit and anticoagulation use will be collected along with any serious adverse event experience during hospitalization.

#### 8.5 3 Month Follow Up

The final and only study-specific visit will be the 3 month (90 - 120 days) office or telephone visit. The Modified Rankin Scale (mRS) is administered, a review of the subject's health and assessment for serious adverse events will be recorded.

**TABLE 3 DATA COLLECTION**

Assessment	Baseline	Procedure	Post Procedure	Day 7 or Prior to Discharge	3 Month Follow-up
Visit Window	< 8 hours from stroke onset	< 8 hours from stroke onset	0 - 36 hours post procedure	1 day prior or day of discharge/transfer or Day 7	90 - 120 days post-procedure
Informed Consent			X 	X 	X 
Medical History	X				
Vitals	X				
Neuroimaging (CT/MRI)	X		X		
NIHSS	X		X		
mRS	X				X

Procedure and device use data		X			
Serious Adverse Event Collection		X	X	X	X

1 Informed Consent may happen at any time after the procedure but must happen prior to the initiation of the 3 month visit (but may be signed at the beginning of the visit)

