### 3 BACKGROUND

#### 3.1 Overview

Stroke is the second single most common cause of death in Europe accounting for almost 1.1 million deaths each year, based on data from WHO estimated the number of strokes in the year 2000. Furthermore, it has been predicted that stroke incidence will increase to 1.5 million per year by 2025, largely owing to the increasing proportion of elderly individuals.

Ischemic strokes represent approximately 87% of all strokes while the remaining 13% are hemorrhagic. The chief goal in treating acute ischemic stroke is to restore cerebral blood flow as rapidly and safely as possible. Currently there are two approaches to treatment, intravenous (IV) delivery of Tissue Plasminogen Activator (tPA), a thrombolytic agent, and mechanical thrombectomy. Combining IV tPA treatment with mechanical thrombectomy has recently been shown to demonstrate an advantage with good clinical results for patients.

Endovascular treatment using mechanical devices to recanalize the occluded vessel include the use of catheters to directly deliver a clot-disrupting or retrieval device to the thrombus, this includes aspiration catheters, stent-retrievers and other clot disrupting devices. However, withdrawing the clot disrupting devices by mechanical force to perform thrombectomy may increase the risk of vascular intimal injury and the incidence of vasospasm. Therefore, aspirating clot may be preferred to reduce vessel damage during recanalization. Mechanical revascularization using an aspiration catheter as the primary approach to clot removal is commonly performed and

[figure not shown]
sometimes referred to as the ADAPT technique. The ADAPT technique is favored by some physicians because of its potential to be less traumatic to the neurovasculature and improve on time to revascularization compared to stent retrievers.

The MIVI Neuroscience, Inc. CE Marked Q Aspiration Catheter is a family of short, extension catheters introduced through an 8F guide catheter/6F sheath. Aspiration is performed from the short Q Catheter into the guide catheter/sheath. The MIVI Neuroscience, Inc. Q Aspiration Catheter may offer an increased force of aspiration from the larger 8F guide lumen and the potential access to more distal clot with the small Q Catheter lumen.

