# 9 ADVERSE EVENTS

## 9.1 AE Definitions

### Adverse Event (AE):

Any untoward medical occurrence, unintended disease or injury, or untoward clinical signs in subjects, whether or not related to the use of the study device or procedures.

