### Adverse Device Effect (ADE):

An ADE is an adverse event related to the use of a medical device. An event should be considered related to the device when it is the result of: insufficient or inadequate instructions for use or any malfunction of the device.

An event should be considered not related to the device when it is the result of: a pre-existing medical condition, a new illness, injury or condition, or due to medication.

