### 12.2 Investigator Records

The investigator is responsible for the preparation, review, and retention of the records listed below:

- All pertinent correspondence that pertains to the investigation
- Signed and dated informed consent forms
- Serious adverse event information
- Medical history (medications etc.), medical records, progress notes, hospital charts, etc.
- A record of each patient's exposure to the investigational device (e.g. implant, follow up, etc.)
- Documentation of any deviation from protocol
- Signed Investigator's Agreement and curriculum vitae
- The protocol and any amendments

Records are pertinent to regulatory authority's inspection and must be retained for a minimum period of (2) years after the latter of two dates: 1) the date on which the investigation is terminated or completed, or 2) as long as local regulatory authorities in countries conducting the research study require retention.

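### After the procedure the plan asks only for serious adverse events, so a non-serious procedure- or device-related event first noted in hospital is requested nowhere

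*Combined protocol and SAP*

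**What the plan says.** Section 8.3 sets out what is recorded about the thrombectomy. One item is "Procedure and device-related adverse events or any device related problems", with no limit to serious events.

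Table 3 has one row for adverse events, "Serious Adverse Event Collection". It is marked at Procedure, Post Procedure, Day 7/discharge and 3 months. A separate row, "Procedure and device use data", is marked at Procedure only and does not mention adverse events.

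For the hospital stay, section 8.4 asks for "Serious Adverse Event monitoring including worsening symptoms/new symptoms" and later again for serious events. Section 8.5 asks for serious events at 3 months, alongside a review of the subject's health.

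The definitions in section 9.1 carry no seriousness limit. An adverse event is "Any untoward medical occurrence, unintended disease or injury, or untoward clinical signs in subjects", and for the device-related subset, "An ADE is an adverse event related to the use of a medical device".

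The record-keeping sections differ. Section 12.2 has investigators keep "Serious adverse event information", while section 12.3 has the sponsor keep adverse events and complaints without qualification.

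**The concern.** Section 4.1 gives the purpose as demonstrating the safety and performance of the catheter, and section 5.3 says that no clinical investigation data exist yet. A reader of the final report will therefore look at the descriptive account of procedure- and device-related harm, not only at symptomatic intracranial haemorrhage.

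Much of that harm can fall short of the seriousness criteria in section 9.1. An access-site problem noticed the day after the procedure, which settles without lengthening the stay or needing intervention, is one example. Vessel effects are another: section 3.1 says that withdrawing clot-disrupting devices "may increase the risk of vascular intimal injury and the incidence of vasospasm" and offers this as a reason to prefer aspiration.

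If such events are not requested once the procedure is over, a short list of related events in the report may reflect what was asked for and not what happened. Consent may come as late as the 3-month visit, and no study data may be collected before it (section 7.2). Procedural and hospital data may therefore be gathered in retrospect, and an event type that is not requested is unlikely to be picked up consistently.

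**Working it through.** The plan states no figure on this point, so the check is to set the sections side by side for each time point.

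| Time point | Serious events | Non-serious procedure- or device-related events |
|---|---|---|
| Procedure | Requested (Table 3) | Requested in 8.3; not named in Table 3, though the procedure-data row may cover them |
| 0–36 hours | Requested (Table 3, 8.4) | Not requested |
| Day 7 or discharge | Requested (Table 3, 8.4) | Not requested |
| 3 months (90–120 days) | Requested (Table 3, 8.5) | Not requested |

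**Procedure.** The two Table 3 rows can be read together: related events of any seriousness as part of the procedural data, plus serious events throughout. They can also be read apart, because the row that names adverse events restricts them to serious ones. This is an ambiguity, not a flat contradiction.

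**After the procedure.** No such reading is available. The procedure-data row is not marked at later time points, and sections 8.4 and 8.5 agree with the serious-event row.

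**Could another section fill the gap?**

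- Section 9.2 limits reporting to the sponsor to serious events and to deficiencies that may have led to a serious device effect. It also has the investigator judge seriousness, which presupposes looking at non-serious events, but it does not say that these are recorded.
- Section 9.3 covers defects, breakage and failure to perform, whatever their seriousness. It concerns the device. A harm that occurs with a catheter working normally is outside it.
- Section 12.3 says what the sponsor retains, not what sites are asked to supply.
- The day-1 imaging and NIHSS, embolization to a new territory and the 3-month health review are collected, but none is a record of non-serious related events.

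**Scale.** The documents give no frequency for these events, so the number missed cannot be derived. The only arithmetic available is the weight of one subject: 1/50 = 2 percentage points at the maximum enrolment.

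**The case against.** The strongest reply is that serious-only collection after the procedure is deliberate. It is consistent across sections 8.4, 8.5, Table 3, the sponsor-reporting rule in 9.2 and section 12.2. The device is CE marked, the procedure is standard of care, and charts may document minor events unevenly. This is a fair account of why a sponsor might choose it. But the protocol never says that it did, and section 8.3, the unrestricted definitions and section 12.3 point the other way.

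A second reply is that relatedness in section 8.3 describes cause and not timing, so a late access-site event could be entered with the procedural data. It could, but section 8.3 is a list of procedural data and nothing tells a site to return to it after the procedure.

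A reader might also infer that Table 3 contradicts section 8.3 outright, and that sites will therefore follow different rules and produce a rate that cannot be interpreted. The documents do not support this. The procedure-data row allows a consistent reading. Sites use sponsor-provided case report forms (section 11.5), are trained on adverse event reporting (11.2) and are monitored (11.6). The forms are not among the documents, so differing site practice is conjecture. Nor are the events beyond recovery: section 12.2 keeps progress notes and hospital charts. They are not requested, which is a narrower statement than that they are lost.

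**Conclusion.** The point holds as a gap after the procedure, with an ambiguity at the procedure itself. As written, no section requests a non-serious procedure- or device-related event first noted at 0–36 hours or by Day 7/discharge. To the extent that such events occur, the descriptive safety summary would understate related harm after the procedure. The size cannot be stated, because the documents give no rate.

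A reader might infer that the study's safety result is compromised. It is not. Symptomatic intracranial haemorrhage, revascularization, embolization to a new territory, functional outcome and mortality are all collected independently of this row. The study also does not test the vessel-injury comparison mentioned in section 3.1, since it has a single arm. What is affected is the descriptive reporting of related events outside the named endpoints.

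The conclusion assumes that the case report form follows Table 3 and sections 8.4 and 8.5. If the form already asks for non-serious related events through discharge, only the protocol wording needs correcting. This is a cheap improvement worth making.

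**What to change.** Reword the Table 3 adverse-event row as *Procedure- or device-related adverse events (any seriousness) and all serious adverse events* at Procedure, Post Procedure and Day 7/discharge. Keep serious events only at 3 months. Make the same change in section 8.4, and bring section 12.2 into line with sections 8.3 and 12.3. The rule in section 9.2 on what is reported to the sponsor can stay as it is, provided that the text separates reporting from recording on the form.

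Dedicated fields for vasospasm, dissection and perforation should be added only if the case report form and the Core Laboratory Manual lack them. Neither is among the documents, so this has to be checked first.

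The cost is a wording amendment, a few form fields at most, slightly more site data entry and a somewhat higher reported event count. No extra visit, procedure or reader is needed. If the sponsor prefers serious-only collection after the procedure, the alternative is to say so and to state in the report that non-serious related events were not sought after that point.
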